4.6. Total number of devices intended for the clinical investigation

Approximately 20 randomized subjects will be included in this clinical investigation and have a TAI procedure performed at V1 and V2 with the investigational device or the comparator device in a randomized order. Following number of investigational devices, comparator devices and Peristeen Plus TAI systems intended for the clinical investigation will be needed:

560 investigational devices (140

these are driving for a high buffer when estimating the total number of the investigational devices needed for this clinical investigation.

- 28 Peristeen Plus rectal balloon catheters
- 64 Peristeen Plus TAI systems.

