5.1. General

The clinical investigation is an exploratory, randomised controlled, open-labelled, crossover investigation (see figure 5). The clinical investigation will be conducted as a multi-centre clinical investigation in two different clinical investigation sites

The total clinical investigation duration for each subject will be up to 17 days, consisting of three site visits: Screening Visit (V0), Baseline Visit (V1) and Visit 2 (V2).

V0 and V1 can be performed on the same day. V1 and V2 must be scheduled on a day where the subject normally performs the TAI procedure, and V2 must furthermore be scheduled within 14 days after V1. At V1 and V2 the TAI procedure will be performed in a hospital setting.

Figure 5: Design of the clinical investigation

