5.4. Rationale for selection and measurement of endpoints

The endpoints and assessment have been selected to support the aim of the investigation exploring the feasibility of performing TAI with the investigational device.

The primary endpoint has been selected to evaluate if it is feasible to use investigational device for TAI to fulfil its intended purpose. Irrigation is defined according to the IFU and must be done with the regular volume of water used by the subject.

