5.7. Randomisation Procedure

All subjects that have given informed consent and meet the inclusion and exclusion criteria will be randomised to one of two treatment sequences:

- First sequence: Investigational device at V1 and comparator device at V2
- Second sequence: Comparator device at V1 and investigational device V2.

The Rave RTSM[™] from Dassault Systèmes/Medidata is a validated computer randomization solution, that will be used for the randomization in this investigation. A randomization will be implemented, in which, subjects are to be randomly assigned to one of two sequences in block sizes of 4.

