6.1.1. Inclusion criteria

For an eligible subject, all inclusion criteria described below must be answered "yes":

Table 1: Inclusion criteria

Inclusion criteria	Justification for inclusion criteria
1. Has given written informed consent	To meet the Helsinki declaration
2. Is at least 18 years old	To meet the Helsinki declaration
3. Has full legal capacity	To meet the Helsinki declaration
4. Has used TAI irrigation with balloon catheter for at least 4 weeks prior to inclusion	To ensure subjects can use TAI and is familiar with the sensation of a balloon catheter to be able to compare with the new rectal cathe- ter
5. Performs TAI minimum 3 times/week	To ensure a homogenous population that performs TAI on a regular basis for comparability within a relative small sample size
6. Is able to follow study procedures assessed by investigator	To ensure study completion of subjects

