10.1. Statistical design, method and analytical procedures

Definition of analysis populations:

Intention to Treat (ITT) and Safety populations will be defined at a formal data review meeting before database lock. As a minimum, the data manager, the clinical manager and the statistician will be involved in the classification of subjects.

The ITT population (full analysis set) will be constituted by all subjects with valid informed consent who have been exposed to at least one Test product, with information on at least one endpoint or assessments used to evaluate the primary or secondary objective.

The Safety population will constitute by subjects who have given informed consent.

All evaluations of endpoint and assessments will be based upon the ITT population whereas adverse events and device deficiencies will be assessed based on the safety population. Invalid individual data points may be omitted from evaluations even though the corresponding subject is part of the ITT population. Any exclusion of data points will be documented.

Considering the data obtained it might be considered to make additional explorative analyses based on a subset of the ITT population.

Evaluation of endpoints and assessments:

All baseline measurements, endpoint and assessments will be summarized by descriptive statistics and/or listed. Endpoint and assessments will be summarized by product, if relevant.

Descriptive statistics for continuous variables are presented with N, Mean, SD (standard deviation), Median, Min and Max, where N denotes the number of subjects contributing with non-missing data. For discrete variables, descriptive statistics are presented with N and percentage, where percentage is based on the total number of subjects/observations with non-missing data.

As an exploratory analysis to support the aim of the investigation the proportion of successful irrigations will be compared for the two type of devices by a one-sided Fisher's Exact Test testing if the proportion with the investigational device is lower than with the Comparator device. The test will be performed on a 5% test level.

Other summaries and analyses can be made, if relevant.

As it is an exploratory clinical investigation no adjustment for multiple testing will be applied if statistical analyses are performed.

All statistical analyses and summaries are made with SAS version 9.4 (SAS Institute Inc., Cary, NC) /Enterprise Guide version 7.1.

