10.2. Sample size

As this is an exploratory clinical investigation no formal sample size calculation has been performed. It is assumed that 20 randomized subjects will be adequate for obtaining indications on performance and feasibility, and we aim to have an equal distribution between neurogenic and functional subjects.

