10.3. Level of significance and power

For Fisher's Exact Test a one-side 5% test level will be applied. As this is an exploratory investigation no power has been applied, when evaluating the sample size. If other explorative statistical analyses are performed a significance level of 5% will be applied.

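### The only named test, a one-sided Fisher's exact test, treats the crossover's paired irrigations as independent groups and can lose sensitivity to inferiority of the new catheter

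*Combined protocol and SAP*

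**What the plan says.** Section 5.1 sets the design: "The clinical investigation is an exploratory, randomised controlled, open-labelled, crossover investigation". Section 4.6 says that about 20 randomised subjects will "have a TAI procedure performed at V1 and V2 with the investigational device or the comparator device in a randomized order". Section 5.7 gives the two sequences, one being "First sequence: Investigational device at V1 and comparator device at V2" and the other its mirror image. Section 5.2 records the primary endpoint, whether irrigation was possible (yes or no), at both visits.

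For inference, section 10.1 names one analysis: "the proportion of successful irrigations will be compared for the two type of devices by a one-sided Fisher's Exact Test", with the alternative that success is lower with the investigational device. Section 10.3 repeats it: "For Fisher's Exact Test a one-side 5% test level will be applied". Everything else is descriptive. Section 10.1 leaves room for further analyses but names none, and no paired, period or sequence method appears elsewhere. Sections 10.2 to 10.4 state that there is no sample size calculation, no power and no success criterion.

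**The concern.** Fisher's exact test on device by outcome compares two independent groups. Here the two groups are the same people, and the test discards which subject failed with which device. That is the information a crossover is run to collect: failures confined to the new catheter count against it, whereas failures by the same subjects with both devices do not.

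The plan's own reasoning is also within-subject. Prior balloon-catheter use is required so that subjects are "familiar with the sensation of a balloon catheter to be able to compare with the new rectal" catheter (section 6.1.1).

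If a subject's two results are positively correlated, the unpaired test is too conservative, and the one-sided alternative looks specifically for inferiority. Positive correlation is plausible. Irrigation "must be done with the regular volume of water used by the subject" (section 5.4), so each subject carries the same volume into both visits, and section 10.2 mixes bowel-dysfunction types: "we aim to have an equal distribution between neurogenic and functional subjects". This is the only prespecified inferential comparison, it is on the primary endpoint, and the device is first in human. The practical risk is that a non-significant result is taken as reassurance.

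**Working it through.** The plan gives no power or effect size, so there is no figure of its own to reproduce.

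**Inputs from the plan.** 20 subjects (10.2), one irrigation per device (4.6, 5.7), binary endpoint (5.2), one-sided 5% (10.3).

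**Assumed, because the plan gives none.** Success rates, within-subject (phi) correlation, no period effect and, except in step 5, complete pairs.

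**Notation.** *b* = subjects failing only with the investigational device; *c* = subjects failing only with the comparator.

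**1. Same proportions, different pairings.** Take 7 investigational failures (13/20 success) and 2 comparator failures (18/20).

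Fisher: p = Σ(x = 7 to 9) C(20,x)·C(20,9−x) / C(40,9) = (14,728,800 + 2,519,400 + 167,960) / 273,438,880 = 0.064.

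Exact McNemar: p = P(X ≥ b), with X ~ Binomial(b + c, 0.5).

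| Fail both | b | c | Fisher p | McNemar p | Paired difference, points (95% score interval) |
|---|---|---|---|---|---|
| 2 | 5 | 0 | 0.064 | 1/32 = 0.031 | −25 (−46.9 to −4.9) |
| 1 | 6 | 1 | 0.064 | 8/128 = 0.0625 | −25 (−48.8 to 1.1) |
| 0 | 7 | 2 | 0.064 | 46/512 = 0.090 | −25 (−50.7 to 4.9) |

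Fisher cannot tell these three datasets apart. The tests can also disagree the other way: 14/20 against 19/20 with b = 6, c = 1 gives Fisher 0.046 and McNemar 0.0625.

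**2. How many datasets are affected.** Of the 1771 possible four-cell tables for n = 20, 49 fall on opposite sides of 5%: 27 significant by Fisher only and 22 by McNemar only. This counts tables without weighting them by probability.

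**3. Type I error.** Summing exact multinomial probabilities over all 1771 tables, for equal success of 50% to 98% and correlation 0 to 0.8, Fisher's error is at most 2.7%. At 80% success it falls from 2.3% (correlation 0) to 0.9% (0.3) and 0.3% (0.5); McNemar gives 1.7%, 1.1% and 0.5%. At 70% and correlation 0.4 the figures are 0.7% for Fisher and 1.3% for McNemar.

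**4. Power.** Same enumeration. With failure rates q₁ and q₂ and correlation ρ, P(fail both) = q₁q₂ + ρ√[q₁(1−q₁)q₂(1−q₂)]. For 60% against 85% and ρ = 0.4 this is 0.060 + 0.4 × 0.175 = 0.130. That leaves 0.270 failing only with the investigational device, 0.020 only with the comparator and 0.580 with neither.

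| Success, investigational vs comparator | Correlation | Fisher | McNemar |
|---|---|---|---|
| 60% vs 85% | 0 | 44.0% | 38.5% |
| | 0.2 | 42.9% | 44.3% |
| | 0.3 | 42.1% | 48.1% |
| | 0.4 | 41.1% | 52.6% |
| 75% vs 95% | 0 | 37.6% | 32.9% |
| | 0.2 | 35.5% | 35.2% |
| | 0.3 | 34.2% | 36.2% |
| 80% vs 98% | 0.2 | 28.5% | 28.5% |

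The paired test gains only above a correlation of roughly 0.2.

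**5. Incomplete pairs.** Assume 18 complete pairs plus one single-visit subject per device, with Fisher on all data and McNemar on pairs only.

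| Success | Correlation | Fisher | McNemar |
|---|---|---|---|
| 60% vs 85% | 0.4 | 38.8% | 44.5% |
| 60% vs 85% | 0.2 | 40.5% | 38.6% |
| 75% vs 95% | 0.3 | 30.8% | 28.3% |

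**The case against.** The strongest reply is that the choice may hardly matter here. Subjects are established balloon-catheter users, irrigate with their usual volume and are treated by experienced staff, so comparator success may be close to 100%. With no comparator failures the two tests never disagree, and both need 5 investigational failures. With one comparator failure they disagree in one table of 40, and there it is Fisher that rejects. At 75% against 95% a correlation of 0.4 cannot even occur (the maximum is about 0.397). Fisher has the edge at low correlation and uses single-visit subjects, whom the ITT definition admits. The comparison is labelled exploratory, feeds no decision rule, and the data will not support conformity assessment. The inclusion rationale concerns the sensation of a balloon catheter rather than whether irrigation was possible. A milder remedy would keep Fisher and add the paired table.

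All of this is right on the facts, and it limits the size of the concern. It does not make an independent-groups test suit paired data. If the tests agree near the ceiling, little is lost by naming the paired one; if comparator failures occur, the paired test is the one that uses them properly. The permission for further analyses does not commit anyone to a paired method and leaves the choice until the data are known. A Fisher-type test on discordant pairs by sequence (Mainland-Gart) would respect the design, but section 10.1 compares proportions by device, which is a different test.

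**Conclusion.** The concern holds. As written, the one named test does not match the crossover: its p-value ignores the pairing, and it can miss inferiority of the investigational device. It does not inflate false positives over the range examined (correlation 0 to 0.8).

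The effect on power runs from a small advantage for Fisher at zero correlation (44.0% vs 38.5%), through equality near the ceiling, to an advantage of 11.5 points for McNemar (52.6% − 41.1%) at 60% against 85% and correlation 0.4. All these rates and correlations are assumptions. The mismatch between test and design does not depend on them. Because the analysis is exploratory with no success criterion, the consequence is confined to how this comparison is read. It should be fixed, but it does not undermine the descriptive primary objective.

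**What to change.** In sections 10.1 and 10.3, replace Fisher's test with wording such as:

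> In subjects with a primary-endpoint result for both devices, a one-sided exact McNemar test at the 5% level will test whether failure only with the investigational device is more frequent than failure only with the comparator.

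Report the four-cell paired table and the paired difference in success with a 95% confidence interval, for example a score interval. Keep single-visit subjects in the by-device descriptive proportions and state how many there are. State also that this test is restricted to complete pairs, because section 10.1 otherwise bases endpoint evaluations on the whole ITT population. A period-adjusted (Mainland-Gart) analysis is optional; with few discordant pairs it has little power.

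The cost is a few sentences and one table, with no new data. The price is that single-visit subjects leave the test, which in two of the three incomplete-pair scenarios above costs about 2 points of power relative to Fisher on all data.

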1.2. Investigators

Details of sites and Principal Investigators (PI) are listed in the list below.

COORDINATING PRINCIPAL INVESTIGATOR	PRINCIPAL INVESTIGATOR		

2. Justification for conducting the clinical investigation

This is an exploratory clinical investigation (first in human) investigating the feasibility and performance of a new rectal catheter for TAI procedure.

Based on recent consensus, TAI should be considered as a therapeutic modality for patients with bowel dysfunction failing to respond to conservative bowel management (e.g., laxative and diet), before resorting to invasive interventions (such as antegrade enemas, sacral nerve stimulation and stomas)¹⁻⁷. This was also one of the conclusions in a meta-analysis comparing treatments for faecal incontinence⁸. The main components of the Coloplast A/S produced Peristeen Plus TAI system consist of a control unit (featuring a pneumatic bulb pump and a four-position rotary switch), a water bag (featuring a pressure relief valve) and a pre-coated rectal balloon catheter or cone catheter.

The data will not be used for conformity assessment; therefore, the study will be submitted to the Danish Ethical Committee (EC) under Article 82 of the Medical Device Regulation EU 2017/245.

3. Objectives

The aim of this clinical investigation is to explore the feasibility of performing TAI by using the newly developed investigational device, CP362 rectal test catheter, compared to the CE-marked Peristeen Plus rectal balloon catheter.

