3.1. Objectives

Primary objective:

The primary objective is to obtain indications that a new rectal catheter can be used for TAI.

Secondary objective:

The secondary objective will include assessment of safety

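### Section 10.1 tests a paired yes/no primary endpoint with an unpaired one-sided Fisher test and plans no confidence interval

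*Combined protocol and SAP*

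**What the plan says.** Section 5.7 randomises each subject to one of two sequences, and each sequence contains both devices. Section 5.2 records the yes/no primary endpoint after irrigation at V1 and again at V2. A subject who completes therefore contributes one outcome per device.

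In Section 10.1, "the proportion of successful irrigations will be compared for the two type of devices by a one-sided" Fisher's exact test at the 5% level, "testing if the proportion with the investigational device is lower than with the Comparator device". The comparison is labelled exploratory. The rest of the planned output is descriptive:

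- "All baseline measurements, endpoint and assessments will be summarized by descriptive statistics and/or listed"
- "Endpoint and assessments will be summarized by product, if relevant"
- "For discrete variables, descriptive statistics are presented with N and percentage"

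No confidence interval, within-subject table or paired method is named. A closing sentence leaves room for other summaries and analyses but specifies none. The ITT set takes subjects "exposed to at least one Test product, with information on at least one endpoint" or assessment, so a subject with an outcome on only one device can be included.

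Section 3 states the aim as exploring feasibility with the new catheter "compared to the CE-marked Peristeen Plus rectal balloon catheter". Section 3.1 words the primary objective without a comparison: "The primary objective is to obtain indications that a new rectal catheter can be used for TAI". Sections 10.2 to 10.4 state that there is no sample size calculation, no power and no success criterion.

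**The concern.** Fisher's test treats the 20 irrigations per device as coming from two unrelated groups. When the comparator also has failures, it returns the same p-value whether the same subjects failed on both devices or different subjects did, although the within-subject evidence differs.

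It is also the only inferential analysis named for the comparison in Section 3, and its alternative is that the new device is worse. A non-significant result counts against a very large deficit but is likely under a moderate one. Without an interval, the report would not show which shortfalls the data still allow. The plan does not say that non-significance will be read as feasibility, so the point is limited to the choice of test and the missing interval.

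**Working it through.** **Inputs.** From the documents: 20 randomised subjects (Section 10.2), hence 20 irrigations per device if all complete; one-sided 5% level (Section 10.3). There is no planned power or rate to reproduce. No success rates are given, so I assume comparator rates of 100%, 95% and 90%, because Section 6.1.1 requires established balloon-catheter users. For the investigational device I assume 80%, 70% and 60%.

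**1. Where Fisher becomes significant.** The one-sided p-value is the hypergeometric tail for failures on the investigational device. With comparator 20/20 and four investigational failures, p = C(20,4)/C(40,4) = 4,845/91,390 = 0.053. With five, p = C(20,5)/C(40,5) = 15,504/658,008 = 0.024.

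| Comparator | Not significant | Significant |
|---|---|---|
| 20/20 | 16/20, p = 0.053 | 15/20, p = 0.024 |
| 19/20 | 15/20, p = 0.091 | 14/20, p = 0.046 |
| 18/20 | 13/20, p = 0.064 | 12/20, p = 0.032 |

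**2. How often a true shortfall is missed.** Sum Binomial(20, p_inv) × Binomial(20, p_comp) over all outcomes with Fisher p > 0.05, treating the devices as independent:

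| True investigational rate | Comparator 100% | 95% | 90% |
|---|---|---|---|
| 80% | 63% | 79% | 89% |
| 70% | 24% | 46% | 66% |
| 60% | 5% | 19% | 38% |

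If every comparator failure also fails the investigational device, a true 80% is missed 85% of the time (comparator 95%) or 97% (comparator 90%).

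**3. What intervals would show.** Clopper-Pearson 95% intervals for one device are 83.2% to 100% for 20/20 (lower limit 0.025^(1/20) = 0.832), 68.3% to 98.8% for 18/20 and 56.3% to 94.3% for 16/20. The Newcombe paired 95% interval for the difference (investigational minus comparator) is -16.1 to +16.1 points at 20/20 against 20/20, and -41.6 to +0.1 at 16/20 against 20/20.

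**4. Where pairing matters: 13/20 against 18/20.** Fisher gives [C(20,7)C(20,2) + C(20,8)C(20,1) + C(20,9)]/C(40,9) = 17,416,160/273,438,880 = 0.064 for any within-subject pattern. The unpaired Newcombe interval is -47.9 to +1.3 points.

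The exact one-sided McNemar p-value is the Binomial(m, 0.5) tail on the m discordant pairs. The paired Newcombe lower limit is D - √[(p1 - l1)² - 2φ(p1 - l1)(u2 - p2) + (u2 - p2)²], with Wilson limits l and u and continuity-corrected φ; the upper limit is analogous. Here p1 = 0.65 (0.433 to 0.819), p2 = 0.90 (0.699 to 0.972) and D = -0.25.

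| Both succeed, only investigational, only comparator, both fail | φ | McNemar p | Paired 95% interval |
|---|---|---|---|
| 13, 0, 5, 2 (both comparator failures shared) | 0.28 | 0.5⁵ = 0.031 | -45.9 to -2.7 |
| 11, 2, 7, 0 (failures in different subjects) | -0.245 | 0.090 (7 of 9 discordant) | -49.5 to +4.2 |

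For the first row, the lower limit is -0.25 - √(0.0471 - 0.0087 + 0.0052) = -0.459. Without the correction to φ the first interval is -44.5 to -5.5; the second does not change.

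**5. Where pairing does not matter.** With comparator 20/20, the paired and unpaired intervals coincide and both tests need five investigational failures (McNemar: 4 to 0 gives 0.063, 5 to 0 gives 0.031).

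**6. Does McNemar detect more?** Exact enumeration of the 2x2 table gives these probabilities of a significant result:

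| Comparator vs investigational | Failures | Fisher | McNemar |
|---|---|---|---|
| 95% vs 80% | independent | 21% | 18% |
| 95% vs 80% | comparator failures all shared | 15% | 17% |
| 95% vs 70% | independent | 54% | 49% |
| 95% vs 70% | comparator failures all shared | 53% | 59% |

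**The case against.** The strongest reply has several parts.

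- **The miss rates reflect 20 subjects, not the test.** This stands. The plan disclaims power, and McNemar is less sensitive than Fisher when failures are independent. The miss rates show why a p-value alone says little here; they are not a cost of leaving out pairing.
- **Fisher is not anti-conservative here.** This stands for the cases computed: with both devices at 95% or both at 90%, it flags under 1% of trials, whether failures are independent or fully shared. The fault is a mismatch with the design, not inflated false positives.
- **Pairing matters only if the comparator fails, which may be rare in established users.** This stands for the test. The missing interval matters in either case. The 13/20 against 18/20 example is chosen to show that pairing can matter, not as a forecast.
- **The plan allows other analyses, and readers can compute intervals from N and percentage.** This stands in part. Permission is not a plan, and Section 5.8 leaves the biostatistician unblinded. Counts per device yield only unpaired intervals; the paired one needs the cross-table or a subject listing, and the descriptive wording does not guarantee a listing.
- **The primary objective is non-comparative and nothing is decided on the p-value.** True: the proportion per device addresses feasibility directly. But Section 3 states a comparison, and the plan chose to prespecify a 5% test for it. Without a pass/fail rule, estimation carries the result.
- **McNemar ignores period.** True, and Fisher ignores it as well.

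**Conclusion.** The concern holds. Section 10.1 prespecifies a test for independent groups on outcomes that are paired by design, and it plans no interval for either device or for the difference. The text on this test reads as complete, so removed material does not explain the gap.

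The missing interval is the larger part. A non-significant 16/20 against 20/20 would be reported without showing that a deficit of about 42 points is still compatible with the data. The choice of test changes the reading only when the comparator has failures. The intervals and p-values follow from 20 complete pairs; the miss rates and detection probabilities also rest on assumed success rates. Because the analysis is exploratory and no decision rule depends on it, this should be corrected but does not undermine the study.

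**What to change.** Amend Section 10.1 to:

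1. Report each device's success proportion with a two-sided 95% Clopper-Pearson interval, using all ITT subjects with an outcome on that device.
2. For subjects with both outcomes, report the within-subject 2x2 table and the paired difference with a 95% Newcombe paired interval.
3. Replace Fisher's test with a one-sided exact McNemar test, still labelled exploratory.
4. State that a non-significant result is not evidence of feasibility or similarity.

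No threshold is needed, so Section 10.4 can stay as it is.

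The cost is wording, one table and interval columns, with no new data or visits. There are three drawbacks. Results will look less certain: even 20/20 on both devices leaves a shortfall of up to 16 points compatible with the data. The paired analysis drops subjects with a single device outcome, though item 1 keeps them. McNemar sometimes needs more failures to reach significance: with one comparator failure in a different subject it needs 7 investigational failures against Fisher's 6, and with two it needs 9 against 8.
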